**Figure 2: Data acquisition process Part A (face-to-face)**

Patient self-administered/ reported	Clinician- reported	Clinical examination

 
• MDADI
 
• UW-QOL V4.0
 
• CPS
 
	
 
• PSS-HN
 
• Functional IDDSI Diet Score
 
	
 
• 100ml WST
 
• FEES-DIGEST
 

**Table 3: Data acquisition process Part A (remote consultation)**

Patient self-administered	Clinician- reported	Clinical examination

 
• MDADI
 
• UW-QOL V4.0
 
• CPS
 
	
 
• PSS-HN
 
• Functional IDDSI Diet Score
 
	
 
• 100ml WST
 

Please see below a description of each data collection tool:

1. The MDADI is a validated and reliable self-administered questionnaire for evaluating the impact of oropharyngeal dysphagia on QoL in HNC patients. The questionnaire consists of 20 questions. Patients rate their responses to statements included on the MDADI on a 5-point scale from “strongly agree” to “strongly agree”. There are 5 subscales. The first is a single, global subscale question to understand the impact of swallowing problems on quality of life. The other subscales address emotional, functional, and physical problems. The global question is scored individually and the other subscales are scored and the mean score is calculated. The mean score is then multiplied by 20 to calculate the composite total score which can range from 0, indicating very low functioning, to 100, indicating extremely high functioning.
2. The PSS-HN is a clinician rated instrument where each subscale (Normalcy of Diet, Eating in Public and Speech Intelligibility) is rated from 0 to 100, with higher scores indicating better performance. The PSS-HN has been shown to have good inter-rater reliability and sensitivity to differences in performance and change over time. See appendix 1 for standard operating procedure.
3. The IDDSI functional diet score is a clinician rated measure of dysphagia severity based on the degree of diet texture restriction. See appendix 2 for standard operating procedure.
4. The 100ml WST is a simple, repeatable measure of swallowing efficiency. This measure has been previously validated in the head and neck population, and the quantitative measures derived from this test, can be used as a measure of swallow performance over time. Patients are asked to drink 100ml of water as quickly and as comfortably as possible- swallow volume, capacity and speed are calculated by timing the test and counting the number of swallows completed by the participant. See appendix 3 for standard operating procedure.
5. The DIGEST-FEES is a rating scale used to report on swallowing safety and efficiency as observed during a Fibreoptic Endoscopic Evaluation of Swallowing (FEES). FEES is an SLT led

endoscopy procedure which involves the use of a fibreoptic scope which is passed transnasally into the participant's pharynx by a trained SLT. The patient is given some food and liquids so that swallowing function can be measured in terms of swallowing safety and swallowing efficiency. The summary DIGEST rating aligns with National Cancer Initiative's framework for toxicity reporting in oncology trials and assigns a global rating of pharyngeal swallowing function according to the interaction of the safety and efficiency profile scores. See appendix 4 for standard operating procedure.

6. The UW-QOL v4.0 is a validated QoL tool examining 12 QoL domains including pain, appearance, activity, recreation, swallowing, chewing, speech, shoulder function, taste, saliva, mood and anxiety. In this tool, each question is scaled from 0 (worst) to 100 (best) according to the hierarchy of response. It also has two global questions about their health-related and overall QoL. In addition, it is possible to calculate a composite score of physical and social-emotional functioning (Rogers et al 1999). The UW-QOL questionnaire is a self-administered scale and each of the categories has several options within it that allow the patient to describe their current functional status. Patients also have the opportunity to select up to 3 options from the 12 domains that are most important to them. The questionnaire relates to the previous 7 days.
7. The CPS is a previously validated tool to assess patients' priorities among potential functional outcomes following treatment for head and neck cancer. Participants will be given a list of 12 statements; including 'being cured of my cancer', 'living as long as possible', 'having no pain', 'being able to swallow all foods and drinks', 'having a normal amount of energy for me', 'returning to my activities as soon as possible', 'having my speech understood easily', 'keeping my natural voice', 'having a comfortably moist mouth', 'keeping my appearance unchanged', 'being able to chew normally' and 'keeping my normal sense of taste and smell'. Patients will be asked to rank each priority from 1-12 where the most important priority is ranked number 1 and the least important number 12.

The multi-dimensional outcome measures will include all routine measures of swallowing function used at our centre currently. The UW-QOL V4.0 and CPS assessment will be in addition to standard of care assessment by the SLT team.

Please see table 4 for data acquisition plan:

**Table 4: data acquisition time points part A**

Timepoint	Measure	Domain	Endpoint
Baseline, 3, and 6 months	MDADI	Swallowing related QoL	Composite score
	UW-QoLv4	Health related QoL	Composite scores of physical and social-emotional functioning are derived from 12 domains. Patients can also highlight up to 3

			priority concerns from the previous 7 days
PSS-HN	Normalcy of Diet, Eating in public and speech intelligibility	Score for each subset	
100ml WST	Swallowing function	Swallowing capacity score (mls/second)	
Functional IDDSI diet score	Diet modification	Diet score (1-8)	
FEES- DIGEST (only if patient is attending for a face-to-face appointment	Swallowing toxicity rating	Summary score (0-4)	
Baseline & 6 months	Chicago priority scale	Patient priority rating of treatment outcomes	Ranked 1-12 priorities

#### Part B

Following informed consent, a proportion of the sample in Part A (prospective cohort), a number of patients who have undergone surgery at least one year ago/ or commenced palliative treatments within the past 12 months (retrospective cohort) and also carers from both patient cohorts will be invited to take part in interviews via video consultation. The interview with patients/ carers will take place at a time that is convenient to both the patient and carers. Participants to be included in Part B will also be identified via PICs.

For the prospective patient cohort who are also participating in part A of the study the interview will take place after the measures have been collected in Part A on a day which is convenient to the participants. Semi-structured interviews will be completed with a member of the research team and will include a number of questions detailed in the topic guide directed towards the research aim in order to promote discussion and identify key swallowing, communication and QoL priorities and concerns. The topic guide has been developed from previous literature and via consultation with the project's Patient-Public Steering Group (please see section 13 on PPI). For the prospective cohort the interview will be completed at baseline and again at 6 months following or into treatment.

For the retrospective cohort the interview will take place for both patient and carers at a single timepoint at least 12 months post surgery or within 12 months of commencing palliative treatments.

The interviews will take place remotely either via telephone or video consultation. The interviews will be anonymised and transcribed verbatim. Please see section 11 for description on how the data will be analysed.

## 10. Sample size

---

### Part A

Part A: The sample size calculation is based on the primary endpoint, change in MDADI scores from baseline and 6 months following diagnosis/treatment of recurrent disease. Previous data has shown that a 10-point between-group difference in MDADI score is clinically significant (Hutcheson et al 2016). This end point has not been measured systematically previously in recurrent disease patients.

Pilot data collected at the Royal Marsden Hospital available for a service evaluation was used to look MDADI score in this cohort of patients. Data based on 10 patients shows a mean composite score of 66.50 at baseline and 52.60 at 6 months with a standard deviation of the difference of 23.68.

With a two-sided alpha of 5% and 95% power a total of 40 participants will be required to complete the paired questionnaires at baseline and 6 months post-treatment (power function, STATA). An additional 4 patients will be recruited to cover for 10% drop out for a total sample of 44 patients. Seventy-five patients are referred to the Royal Marsden Hospital per year with recurrent OPC and this number is set to increase with the on-going developments in robotic surgery, experimental trials and the development of the International Centre for Recurrent Head and Neck Cancer (IReC). Data collection will take place over an 18-month period.

### Part B

Given that this study is qualitative and exploratory, a sample size calculation is not required. Expected recruitment rates include approximately 20-30 patients and 10-20 carers or until data saturation occurs- please see data analysis plan in section 11.

## 11. Data analysis

---

A consort flow diagram will be produced to describe the flow of patients through the study

### Part A

Baseline patient characteristics (age, gender, ethnicity and previous HNC treatment history) will be summarized in addition to the diagnostic and treatment details (site of recurrence, type of treatment, use of reconstruction, tracheostomy, feeding tube presence/ type) using descriptive statistics.

The primary endpoint data will be analysed to compare the mean change from baseline MDADI composite score to 6 months into or post treatment using a two-sided paired t-test if data are normally distributed. In the event of not normally distributed data non-parametric-methods (Wilcoxon Signed Rank test) will be used.

Secondary endpoints (PSS, 100ml WST, IDDSI functional diet score, FEES-DIGEST and UW-QOL, and CPS scores) will be summarised using summary statistics (mean with standard deviation if data are normally distributed or median with IQR if data have a skewed distribution). Counts and percentages will be presented with 95% confidence intervals.

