## 2. Rationale

---

To enable people to make informed choices about the range of treatments available for recurrent OPC, detailed information is required on the likely trajectory of functional and QoL change during or following treatment. Patient experience data is essential for any research so that relevant QoL endpoints can be identified, appropriate outcome data can then be collected and thus meaningful data can be presented to patients during the decision-making process (Blanchard et al 2016). This project will aim to address the gaps in the literature with regards to both functional and QoL outcome data and patient/ carer experience of the functional changes in communication and swallowing and overall QoL during and following treatments for recurrent OPC.

The purpose of this study is to understand the lived experience of being diagnosed and living with recurrent head and neck cancer and how functional and QoL changes are prioritised by patients. This study will also measure the trajectory of swallowing, communication and QoL change for people undergoing treatments for recurrent OPC.

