### Secondary endpoints

1. MDADI composite score at baseline and 3 and 6, months following surgical or re-irradiation treatment or 3 and 6, months into non-surgical treatment.
2. Mean PSS-HN Normalcy of diet, public eating and speech intelligibility using the PSS-HN scale scores at 3 and 6 months .
3. Median (IQR) IDDSI functional diet score International dysphagia diet standardisation initiative functional diet scale (IDDSI-FDS) at baseline and 3 and 6 months following surgical or re-irradiation treatment or 3 ad 6,months into non-surgical treatment.
4. Mean 100ml WST capacity score score at baseline and 3 and 6, months following surgical or re-irradiation treatment or 3 and 6 months into non-surgical treatment.
5. FEES DIGEST summary score at baseline and 3 and 6 months following surgical or re-irradiation treatment or 3 and 6months into non-surgical treatment.
6. Mean UW-QoL4 composite physical, social and functional scores at baseline and 3 and 6 months following surgical or re-irradiation treatment or 3 and 6 months into non-surgical treatment.
7. Number and percentage of patients ranking of CPS categories (1-12) in order of importance, at baseline and 6 months following surgical or re-irradiation treatment or 6 months into non-surgical treatment
8. Number and percentage of patients still alive at the end of the study
9. Number and percentage of patients using a gastrostomy at each time point at baseline and 3 and 6 months following surgical or re-irradiation treatment or 3 and 6 months into non-surgical treatment.

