### **Part A**

Following informed consent, patients will have all functional and QoL measures collected at their next scheduled outpatient appointment. No additional outpatient appointments or patient contacts will be required for RM patients. All patients are routinely seen by the clinical team at baseline, and for regular follow up including 3 and 6 month clinical reviews, where all measures except the Chicago Priority Scale (CPS) will be repeated. The CPS will be completed at baseline and 6 months only. In the event that social distancing measures remain in place and patients are not attending the hospital for face-to-face review with their clinical team, or if the patient has a preference for remote review, and for participants identified via PICs, a video consultation will be set up so that a minimum set of outcome measures can be collected including the MDADI, and UWQoL4, PSS- HN (all domains), Functional IDDSI Diet Score, CPS and the 100ml WST.

The only measure which cannot be obtained via remote means is the FEES assessment. Please see figure 2 for data acquisition schema.

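### Section 11 names no analysis of the 3-month MDADI, and the primary paired test leaves out patients who have a 3-month score but no 6-month score

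*Combined protocol and SAP*

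**What the plan says.** - **Collection.** Section 9, Part A, describes "regular follow up including 3 and 6 month clinical reviews, where all measures except the Chicago Priority Scale (CPS) will be repeated". Table 4 lists MDADI at baseline, 3 and 6 months.
- **Endpoint.** Section 6, secondary endpoint 1, is the "MDADI composite score at baseline and 3 and 6, months following surgical or re-irradiation treatment", with the same visits counted into treatment for non-surgical patients.
- **Purpose.** Section 2 states: "This study will also measure the trajectory of swallowing, communication and QoL change".
- **Primary analysis.** Section 11, Part A, compares the "mean change from baseline MDADI composite score to 6 months into or post treatment using a two-sided paired t-test", or uses the Wilcoxon signed rank test if the data are not normal.
- **Secondary analysis.** The same section states: "Secondary endpoints (PSS, 100ml WST, IDDSI functional diet score, FEES-DIGEST and UW-QOL, and CPS scores) will be summarised using summary statistics". MDADI is not in the bracket.
- **Missing data.** Section 11 gives no missing-data method, no longitudinal model and no rule for patients who die before 6 months. The withdrawal rule in section 8 keeps data gathered before a withdrawal in use.

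**The concern.** Both primary tests need complete pairs. A patient who was scored at baseline and 3 months and then lost contributes nothing to the primary result, even though the 3-month score shows how that patient was doing. This sits awkwardly with the withdrawal rule in section 8.

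If the patients who had worsened most by 3 months are the ones missing at 6 months, the paired mean understates the fall in swallowing function. That estimate is meant to inform patients choosing between treatments. The plan also leaves open how the 3-month change, one part of the trajectory, will be reported.

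Loss above the 10% allowed for in section 10 is foreseeable. Section 1 cites overall survival of 8 months and 1-year survival of 30.9% on platinum-based combinations, and section 3 includes palliative systemic treatment.

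**Working it through.** **1. The plan's own figure.** Section 10 gives these inputs: "Data based on 10 patients shows a mean composite score of 66.50 at baseline and 52.60 at 6 months", a "standard deviation of the difference of 23.68", and "With a two-sided alpha of 5% and 95% power a total of 40 participants will be required".
- Change: 66.50 − 52.60 = 13.90. Standardised: 13.90 / 23.68 = 0.587.
- Paired t-test, noncentral t: n = 40, power 95.2%. The figure reproduces.
- Dropout: 40 × 1.10 = 44, or 40 / 0.90 = 45 after rounding up. The difference is one patient.
- Standard error with 40 pairs: 23.68 / √40 = 3.74 points.

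**2. How much loss is plausible.** Assume exponential survival and treat the 8 months as a median.
- Dead by 6 months: 1 − 0.5^(6/8) = 41%.
- From the 1-year figure: 1 − 0.309^(6/12) = 44%.
- Both apply only to patients like the platinum-treated group. Their share of this cohort is not stated, so overall loss is unknown.
- Power of the paired test would be 92.8% with 36 pairs and 90.5% with 33.

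**3. Paired mean against model, by simulation.** Cohorts of 44 were simulated. The model estimate regresses the 6-month score on the baseline and 3-month scores in completers, averages the prediction over all 44 patients, and subtracts the baseline mean. This is the maximum-likelihood estimate from an unstructured repeated-measures model when only 6-month scores are missing. The documents give no 3-month mean, per-visit SD or correlations, so two assumed sets were used.
- *Set A:* means 66.5, 50 and 52.6; SD 22; correlations 0.42 (baseline and 3 months), 0.42 (baseline and 6 months) and 0.65 (3 and 6 months). SD of change = √(2 × 22² × 0.58) = 23.7.
- *Set B:* means 66.5, 57 and 52.6; SD 20 or 24. Baseline-to-6-month correlation = 1 − 23.68²/(2 × SD²) = 0.30 or 0.51. The 3-to-6-month correlation is 0.60 to 0.80.

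Bias is the number of points by which the 13.9-point fall is understated:

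| Missingness at 6 months depends on | Missing | Paired bias | Model bias |
|---|---|---|---|
| 3-month worsening (A) | 10 / 20 / 30% | 1.1 / 2.1 / 3.2 | about 0 |
| 3-month level (A) | 10 to 30% | 0.4 to 0.9 | about 0 |
| 3-month level (B) | 10% | 0.2 to 0.7 | within 0.15 |
| 3-month level (B) | 25% | 0.5 to 1.4 | within 0.15 |
| Unseen 6-month score (B) | 40% | 3.8 to 4.7 | 3.1 to 4.5 |

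**4. Why the first two rows differ.** In Set A, the 6-month change falls by 22 × (0.65 − 0.42) = 5.1 points per SD of lower 3-month level. Per SD of 3-month worsening it falls by 22² × (1 − 0.42 − 0.42 + 0.65) / 23.7 = 16.5 points. The ratio is about 3.3, as in the table. The size of the bias therefore rests heavily on the assumed mechanism.

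**5. Precision under random missingness.** Neither method is biased. In Set B the standard error falls about 2 to 4% at 10% missing (for example 3.75 to 3.65) and 10 to 15% at 40%. In Set A the variance falls 5, 10 and 15% at 10, 20 and 30% missing.

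**6. When the 3-month score is missing too.** The results above give every patient a 3-month score. If half of those missing at 6 months also lack it (Set A), the gain almost disappears under the level mechanism: model bias 0.3, 0.5 and 0.9 against 0.3, 0.6 and 1.0 for the paired mean at 10, 20 and 30% missing. Under the worsening mechanism a bias of 0.3 to 0.7 remains in the model.

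**The case against.** **The 3-month score may already be covered.** A reader might infer that the 3-month MDADI enters no analysis at all. The documents do not support that. The sentence on secondary endpoints is general. Its bracket also omits gastrostomy use and survival, which the following sentence on counts and percentages evidently serves, so the list is not exhaustive. A drafting omission is the likelier reading, and visit-by-visit summaries would give a descriptive trajectory. This stands, so the claim is limited to there being no named analysis. Even then, such a summary leaves the 3-month data out of the primary estimate.

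**The paired test fits the plan.** Part A is descriptive and exploratory, the primary endpoint is a two-point difference, and the test matches the sample-size calculation. This stands, and the paired test should be kept.

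**A model does not always reduce bias.** A reader might infer that it does. It does so only if missingness depends on observed scores. With missingness driven by the unseen 6-month score, the two methods are practically equal at about 2.4 to 2.5 points at 30% missing in Set A. In one Set B setting at 40% missing the model is worse (4.3 against 3.9).

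**Deaths.** A model on everyone with a baseline score implicitly projects MDADI after death, and death is a foreseeable cause of loss here. This is the strongest objection to making that model the primary analysis, and it stands.

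**The bias is conservative.** Understating the fall makes the test harder to pass, and 1 point is small beside a standard error of 3.7 and the 10-point between-group benchmark in section 10. That is fair for the test. It is less comforting for an estimate meant to inform patients.

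**Conclusion.** The point holds in a limited form. Section 11 names no analysis of the 3-month MDADI, though the general sentence may be meant to include it, and the primary test discards the earlier scores of anyone without a 6-month score.

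At the planned 10% loss the gain from a model is modest: roughly 0.2 to 1.1 points of bias and a standard error about 2 to 4% lower. At 20 to 30% loss it is about 0.5 to 3.2 points. These sizes rest on assumed 3-month means, SDs, correlations and missingness mechanisms, on a 3-month score for every patient, and on treating all loss alike, without separating death from non-response. Only the non-response of living patients can be recovered without projecting scores after death.

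Two further inferences are not supported: that the paired test is the wrong test for the stated endpoint, and that the sample size is wrong. The 40 pairs reproduce. This is a cheap improvement to the plan and does not invalidate it.

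**What to change.** Amend section 11, Part A:
1. Name MDADI at baseline, 3 and 6 months among the secondary summaries.
2. Keep the paired test. Alongside it, pre-specify a repeated-measures model on the three visits (visit as a categorical effect, unstructured covariance, REML, Kenward-Roger degrees of freedom), reporting the 3-month and 6-month changes from baseline with 95% confidence intervals.
3. State that the model assumes missingness depends only on observed scores.
4. Run the model in patients alive at 6 months, so that the 3-month data of living non-responders are used without projecting scores after death. Run it also in all patients with a baseline score, and label that result as carrying the projection.
5. Report the number of deaths beside both results.

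The cost is a few sentences and a standard command in the software already used for the sample size. No new data or visits are needed. The downside is a little more analysis and one added assumption to state.

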### Primary endpoint

Difference in the mean MDADI composite score at baseline compared to 6 months after surgical treatment or re-irradiation or 6 months into non-surgical treatment

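### A normality check can replace the paired t-test with the Wilcoxon signed-rank test, so the primary p-value may not test the mean change that defines the endpoint

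*Combined protocol and SAP*

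**What the plan says.** - **Endpoint (Section 6, Primary endpoint).** It is defined on means: "Difference in the mean MDADI composite score at baseline compared to 6 months after surgical treatment or re-irradiation", or 6 months into non-surgical treatment.
- **Sample size (Section 10, Part A).** The inputs are a "mean composite score of 66.50 at baseline and 52.60 at 6 months with a standard deviation of the difference of 23.68", from a pilot of 10 patients. The result is "With a two-sided alpha of 5% and 95% power a total of 40 participants will be required" with paired questionnaires.
- **Analysis (Section 11, Part A).** Mean change is to be compared "using a two-sided paired t-test if data are normally distributed". The fallback follows: "In the event of not normally distributed data non-parametric-methods (Wilcoxon Signed Rank test) will be used".

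Section 11 leaves three things open: whether the changes or the raw scores are checked for normality, what test or threshold decides, and what estimate and interval go with the Wilcoxon test. The only confidence intervals it mentions are for counts and percentages.

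**The concern.** Endpoint and sample size both concern a mean, yet the observed data decide which test is primary. The signed-rank test takes the changes to be symmetric about zero under its null. When they are skewed it responds to the pseudo-median (the median of averages of two independent changes), which then differs from the mean. If skewness is what makes the normality check fail, the rule leaves the defined endpoint just when mean and pseudo-median part company.

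Skewed changes are conceivable here. The cohort pools open surgery, transoral robotic surgery, re-irradiation and palliative systemic treatment (Section 8, Sampling) on a scale bounded at 0 and 100 (Section 9), and a minority could fall a long way while most stay stable. The primary p-value might then answer a question other than the stated one, or appear without an estimate of the mean change. Section 2 says the study should inform patients about likely functional change, and that purpose needs the size of the change and its uncertainty.

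**Working it through.** **1. The plan's own figure.** The planned fall is 66.50 - 52.60 = 13.90 and the SD of the difference is 23.68, so the standardised effect is 13.90 / 23.68 = 0.587. For a paired t-test, power comes from the noncentral t distribution with n - 1 degrees of freedom and noncentrality 0.587 × √n:

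- n = 39: power 94.6%.
- n = 40: noncentrality 3.71, critical value 2.023, power 95.2%.

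The stated 40 pairs are therefore the paired t-test answer for a mean change.

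**2. What each test addresses.** The t statistic is the mean change divided by (SD / √n), so it targets the mean. The signed-rank statistic sums the ranks of the absolute changes that are positive, and it is centred correctly only when the changes are symmetric about zero. The two targets agree under symmetry and separate under skewness.

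**3. How far they separate (assumed gamma shapes).** For a gamma with shape k, centred at mean 0 and scaled to SD 23.68, skewness is 2/√k and the pseudo-median is 23.68 × (m/2 - k)/√k, where m is the median of a gamma with shape 2k.

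- k = 16: 23.68 × (31.667/2 - 16)/4 = -1.0
- k = 4: 23.68 × (7.669/2 - 4)/2 = -2.0
- k = 2: 23.68 × (3.672/2 - 2)/1.414 = -2.7
- k = 1: 23.68 × (1.678/2 - 1)/1 = -3.8

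The sign reverses if the long tail is towards large falls.

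**4. Rejection rates at zero mean change.** Monte Carlo, n = 40, two-sided 5%, 8,000 to 20,000 samples per setting. The switch is assumed to be Shapiro-Wilk on the changes at 5%, because the plan names none. Ranges span repeat runs.

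| Assumed shape | Share switched | Two-stage rule | t-test always |
|---|---|---|---|
| Normal | 5% | 5.1-5.5% | about 5% |
| Gamma, skewness 0.5 | 19% | 5.6-5.9% | about 5% |
| Gamma, skewness 1.0 | 58% | 7.8-9.2% | about 5% |
| Gamma, skewness 1.4 | 88% | 12.0-12.4% | about 6% |
| Gamma, skewness 2.0 | 99% | 18.6-19.6% | 6-7% |
| Symmetric, heavy tails (t with 3 df) | about 56% | 5.1-5.2% | about 4.5% |

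**5. A mixed cohort (assumed).** Suppose 75% of changes are normal with mean +8 and SD 12, and 25% are normal with mean -24 and SD 20.

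- Mean: 0.75 × 8 - 0.25 × 24 = 0.
- Variance: 0.75 × (144 + 64) + 0.25 × (400 + 576) = 400, so the SD is 20.
- Third moment: 0.75 × (512 + 3,456) - 0.25 × (13,824 + 28,800) = -7,680, so skewness is -7,680 / 8,000 = -0.96.

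The pseudo-median is about +2 points although the mean is 0. The two-stage rule rejects in about 10-11% of samples and the t-test in about 5.5%.

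**6. At the planned effect.** With a true mean fall of 13.90, SD 23.68 and gamma skewness of 0.5 to 2 towards large falls, the two-stage rule rejects in about 93-96% of samples, close to the planned 95%.

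**The case against.** The strongest reply has four parts.

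- **The inflation is assumed.** The documents give a pilot mean, an SD and n = 10, with no skewness or shape. The gamma shapes, the mixture and the Shapiro-Wilk check are all the reviewer's. A reader might infer that the plan runs its primary test at 8-19% whenever the data are not normal. The documents do not support that: the range needs skewness of about 1 to 2, mild skewness gives about 6%, and symmetric non-normal data give about 5%. This part stands.
- **Wilcoxon is valid for its own null.** A reader might also infer that the test is broken. It is not. When baseline and 6-month scores are exchangeable, the differences are symmetric and it rejects in 4.9-5.3% of samples. The excess is error only against the hypothesis of zero mean change. This also stands, and it makes the problem one of endpoint against test.
- **The practical effect is modest.** Separations of 1 to 4 points are small beside the 10 points that Section 10 treats as clinically significant and the planned fall of 13.9. If the planned effect is real, the conclusion would rarely change (step 6). This limits the importance of the point but does not remove it, because a smaller true change is possible.
- **The rule is conventional, pre-specified and sits in an exploratory study** (Section 4). That lowers the severity. The study nevertheless has one powered primary test at two-sided 5%, and nothing elsewhere in the plan says which quantity is reported after a switch.

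**Conclusion.** The point holds as a mismatch between the primary endpoint and one of its two possible tests. Followed as written, the plan can produce a primary p-value that does not test the stated mean change, with no stated estimate or interval beside it.

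The size is conditional. At n = 40 with zero mean change and Shapiro-Wilk at 5% as the switch, the rejection rate is about 6% at skewness 0.5, 8-9% at 1.0, 12% at 1.4 and 19% at 2.0. The t-test gives about 5-7% over the same shapes, and both stay near 5% under symmetry. Neither the skewness nor the check is in the documents, and the simulated shapes ignore the bounds of the MDADI scale. The figures show direction and plausible size; they do not forecast this trial's error rate. This is a cheap improvement and does not invalidate the design.

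**What to change.** In Section 11, Part A, state that the primary analysis is the mean paired change in MDADI composite score with its 95% CI from the paired t-test, whatever a normality check shows. Add a bootstrap CI as a supporting check if the changes are clearly skewed, and list the Wilcoxon signed-rank test as a sensitivity analysis only. If any normality check is kept, say that it applies to the paired changes and name the test or plot.

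The cost is about one sentence. The sample size stays at 40 pairs (95.2% power), because it was already calculated for this test. The downside is a possible small loss of power if the changes are symmetric but heavy-tailed.
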